Figure 3. In a proof of concept study, VO_2 monitoring of rabbits (weight ~3 kg) undergoing a 30 minute period of observation, followed by a 15 minute period of asphyxia, then a post-asphyxial recovery. Exemplary VO_2 tracings shown of animals treated (blue line) and untreated (red line) with an intravenous formulation of oxygen which prevented severe hypoxemic-ischemic injury. Animals which suffered severe injury exhibited a significant decrement in VO_2 early during the recovery period, a pattern which worsened prior to post-asphyxial loss of circulation. Animals who experienced treated asphyxial injury had an unchanged VO_2 curve. **A central hypothesis of this study is therefore whether VO_2 may represent a sensitive, real-time, prospective, and non-invasive marker of circulatory failure and inadequate DO_2 in newborns at risk for this life-threatening problem.**

measurements, intermittent measurements of lactate and superior vena cava saturations) add power in predicting which patients will experience PLOC.

Hypothesis: Continuous measurements of VO₂ and SVC saturations will add significantly to our ability to predict which patients will undergo PLOC.

Study Design

We will prospectively and continuously measure VO₂ and SVC saturations in newborns undergoing stage I palliation (S1P) or hybrid palliation (HP) for HLHS (n=20) or arterial switch operation (ASO) for d-TGA/IVS (n=20), beginning at the time of first preoperative intubation and ending at the time of the first postoperative extubation. Newborns will be followed for the occurrence of PLOC as the primary endpoint. A study schematic is attached as **Appendix 1**.

Study Population

Inclusion criteria.

1. Patient from birth to 6 months of age
2. HLHS AND no prior operations AND planned S1P or HP
OR
d-TGA/IVS AND planned ASO
3. Written parental informed consent

Exclusion criteria.

1. Weight < 2 kg
2. Disease specific
 - A. HLHS patients: Infants whose surgical plan includes a neonatal biventricular repair will be excluded.
 - B. d-TGA/IVS patients: Newborns with any additional cardiac defect other than an atrial septal defect will be excluded.
3. Patients on ECMO preoperatively
4. Clinically significant tracheo-esophageal fistula or known preoperative air leak

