VO₂ monitoring. Currently, all patients undergoing mechanical ventilation for any reason are monitored using a capnograph, a device which features an adapter fitted onto the end of the endotracheal tube for the continuous monitoring of end-tidal carbon dioxide (EtCO₂), and other basic spirometric measures (e.g. tidal volume, VCO₂, lung compliance). There are several different capnograph devices in current use within BCH. However, none of these devices measure VO₂, which is a critical endpoint in our study. Therefore, patients included in the study will be monitored using a device with this capability (Datex Ohmeda Critical Care Monitor, GE Healthcare, E-CAIOVX module, shown in **Figure 4**). As discussed above, the study team has accumulated significant experience with this FDA-approved device in children, and it has been used in other clinical studies in children at BCH. All cardiac intensive care, cardiac anesthesia and cardiac ICU nursing staff will be inserviced on the equipment by a member of the study team prior to initiation of the study.

Figure 4. The E-CAIOVX module of the GE monitor to be used in this study. The plastic piece to the left fits onto the end of the tracheal tube and measures features of inhaled and exhaled breath by side-stream analysis.

In the opinion of the study team, VO₂ has not been validated as a clinically useful piece of data in this age group. Therefore, only the standard parameters of ventilation (i.e. end tidal CO₂, capnograph waveform, tidal volume and lung compliance measurements) will be displayed on the monitor for clinician use for the duration of the study; VO₂ will be recorded but not displayed on the monitor.

SVC saturation monitoring. Currently, all patients undergoing an S1P, HP or ASO routinely undergo placement of a temporary central venous catheter placed within the internal jugular vein, and terminating within the SVC. These catheters are standardly used for infusion of inotropic medications, constant monitoring of central venous pressures and the intermittent withdrawal of blood for SVC saturation measurements. These catheters are standardly 4 French in size, are 5 cm in length and contain two lumens (Cook Medical). Following admission to the CICU, these catheters are routinely treated with a Heparin infusion at 10 Units/kg/hour through one of the lumens until the time of removal.

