In lieu of the standard Cook Medical catheter, the treating team will place a similar FDA-approved catheter, but which is fitted with a fiberoptic sensor which continuously records the oxyhemoglobin saturation of the blood to which it is exposed. The catheter is 4.5 French, 5 cm in length, has two lumens, and is Heparin bonded (PediaSat catheter, Edwards LifeSciences, Model# XT245HK, see **Figure 5**). The catheter comes with a sterile percutaneous insertion kit. As above, all cardiac intensivists, cardiac anesthesiologists and CICU nursing staff will receive a formal training on the insertion and care of this catheter by the company representative ([name]). Prior to insertion, the catheter will be calibrated using an in vitro solution which comes with the catheter. For those familiar with the device, this process will add 2-3 minutes to the insertion time. Following insertion of the catheter, the device will be attached to the study monitor (Datex Ohmeda Critical Care Monitor, GE Healthcare) via a specialized cable. The catheters will be paid for by the PI.

Figure 5. The PediaSat catheter to be used in this study is functionally the same as catheters routinely used in the perioperative care of newborns with CHD except that it is fitted with a fiberoptic probe at its tip which continuously reads SVC saturation.

In the opinion of the study team, the SVC saturation is a clinically useful piece of data which is routinely used at BCH in the management of patients. Because the device readings have been shown to correlate well with oximetric readings from venous blood, the SVC saturation will be continuously displayed on the study monitor for clinicians to use at their discretion for the duration of the study.

The study will end following the first postoperative extubation or removal of the central venous catheter, whichever occurs last.

Endpoints/Outcomes

Primary Outcome. The primary outcome being measured will be a composite endpoint of PLOC, including the need for CPR, the need for ECMO in the setting of CPR, or death.

Secondary Outcomes. Because Aim 3 of this study is to determine whether the aforementioned oxygen-based measurements add to the predictive power of the data standardly used to assess patients, there will be a substantial amount of data gathered, which is outlined below.

- Oxygen-based parameters unique to this study

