Upon study enrollment, we will record relevant variables for the purposes of comparisons between patients, including gestational age, date and time of birth, gender, weight and length, date of admission, known medical problems, current medication list. Markers of severity of illness will include the number of organ failures, number and dosing of inotropic medications, and any positive cultures.

Adverse events

Although this is a prospective, observational study which do not anticipate will alter our standard practices, we will monitor vigilantly for complications associated with the standard therapies used in these patients for differences in study patients. Namely, we will monitor for endotracheal tube complications (e.g. ventilator associated pneumonia, accidental extubation) and for central venous line complications (e.g. catheter associated bloodstream infections).

Safety end points

Because this is a prospective observational study and is not expected to directly impact patient care, we will not have stopping rules for an individual patient per se, except if informed consent is withdrawn by a parent or team member.

Parameters for discontinuation of the research

All components of this study have been tested and validated in the critically ill newborn population. As such, we do not anticipate any technical problems with the observations proposed in this study. However, the research will be discontinued if an interim analysis shows a significant increase in the adverse events presented above compared with a retrospective control.

Adverse Event Criteria and Reporting Procedures

A data safety and monitoring board (DSMB) will be composed of two clinicians knowledgeable in the postoperative care of children with congenital heart disease. The DSMB for this study will include [name], Director of Respiratory Care, and staff Anesthesiologist and Intensivist at Boston Children's Hospital, and [name], a staff Cardiac Anesthesiologist at Boston Children's Hospital. Meetings will be held at the discretion of the DSMB members and study investigators, at least once following enrollment of the first 5 patients. The following complications will be specifically monitored for and reported to the DSMB immediately upon occurrence: accidental extubation or central venous catheter removal thought to be related to the monitoring devices (these are both extremely unlikely given that they are FDA-approved, widely used devices in children).

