The second standard intervention used here which imposes risk is the insertion of an internal jugular venous catheter, which again is standard practice in newborns undergoing these procedures. The theoretical risks of this FDA approved device are no different from standard catheters, which include bleeding, infection and thrombosis. To address these, the staff within the CVP at BCH utilize an insertion bundle and antibiotic coated catheters, which will be a practice which is unchanged in this study. As per routine in the CICU, the catheters will be infused with a Heparin infusion at 10 Units/kg/ hour through one of the two ports of the line, which will decrease any risk of thrombus formation. The catheters are additionally coated with AMC Thromboshield (a coating containing both Heparin and antimicrobials), which will further decrease the risks of both infection and thrombus formation.

Potential Benefits

Potential Direct Benefits

Because this is a prospective observational study, the measurements are not intended to change the standard of care by which these patients are treated. However, there are several possible direct benefits to patients:

- *Decrease in venous blood sampling.* It is possible that due to the indwelling oximeter that the care team will require fewer blood samples to be tested for SVC saturations. This could potentially decrease the blood loss associated with blood sampling and diminish the risk of infection (which is associated with the number of times a line is entered).
- *Improved assessments of Q_p/Q_s .* As discussed in the background section, the ratio of blood flow to the lungs to that of the body is a vitally important number in the care of patients with HLHS. In the CICU, it is common practice to make changes in patient management based on this value, although the value itself is quite often inaccurately assessed.³ The primary unmeasured variable in the calculation of this ratio is the SVC saturation. The ability to constantly and accurately monitor this value, in combination with arterial saturations based on pulse oximetry, may vastly improve the quantification of the Q_p/Q_s ratio and better inform management decisions at the bedside for critically ill neonates.

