Appendix 1. Study schematic

Appendix 2. Parent informational flyer

Oxy-CAHN Study

Oxygen consumption-based assessments of hemodynamics in neonates following congenital heart surgery

Enrollment Criteria

Preoperative HLHS (n = 20)
OR
d-TGA/IVS (n=20)

Assent of cardiac surgeon and cardiac intensivist
Parental consent

Cardiac OR

At first intubation*

- > Calibrate VO_2
- > Check ETT leak
- > Begin data collection

At CVL insertion*

- > In vitro calibration
- > Catheter insertion
- > Confirm position in SVC

Cardiac ICU

Daily collect:

- > Primary outcome (CPR, ECMO, death)
- > VO_2 and SVC saturations
- > Cardiac output and Q_p/Q_s
- > NIRS, lactate, UOP
- > Inotropes
- > Blood loss and transfusion
- > Sedatives, paralytics
- > Feedings
- > Vital signs

From S5 Collect™

From medical record
and discussion with
primary team

From T3 database

* Enrollment begins at either first intubation or central venous line insertion (whichever occurs first) and ends at first postoperative extubation or central venous line removal (whichever occurs last).

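### Adverse-event capture stops when the last device comes out, so line infections, pneumonias and clots recognised later have no stated route into the safety comparison

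*Combined protocol and SAP*

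**What the plan says.** **End of the study.** Study Treatments, SVC saturation monitoring: "The study will end following the first postoperative extubation or removal of the central venous catheter, whichever occurs last". The footnote to the study schematic agrees, stating that enrollment "ends at first postoperative extubation or central venous line removal (whichever occurs last". The Study Design section differs: it describes measurement as "ending at the time of the first postoperative extubation", with no mention of the line.

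**Abstraction.** Under Outcome measurements, the study team abstracts the chart each day while the study lasts. No section describes safety follow-up after that.

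**Events monitored.** The Adverse events section covers endotracheal tube complications, with ventilator associated pneumonia and accidental extubation as examples, and "central venous line complications (e.g. catheter associated bloodstream infections". Thrombosis is not named there. Risks and Discomforts does name it, giving the theoretical risks of the catheter as those "which include bleeding, infection and thrombosis".

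**The catheter.** Of the usual lines the plan says: "These catheters are standardly 4 French in size". Of the study line: "The catheter is 4.5 French, 5 cm in length, has two lumens, and is Heparin bonded".

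**Use of the events.** Aim 1 hypothesises no rise in equipment-related adverse events, with line displacement and inadvertent extubation as its examples. The research is to be discontinued if an interim analysis shows "a significant increase in the adverse events presented above compared with a retrospective control". The control's source, size, event definitions and observation window are not given.

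**The concern.** Accidental extubation and line displacement are seen when they happen. Pneumonia, bloodstream infection and thrombosis are diagnosed by work-up, so recognition can come later than the event and later than removal of the device. Both the study and its abstraction end when the second device is out, so an event recognised after that point has no stated route into the data.

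Two uses of the data are exposed: the interim comparison that can stop the research, and the infection and thrombosis part of Aim 1's safety conclusion. Missing late events can only lower the study count. Whether that also distorts the comparison depends on how the control is counted, which the plan leaves open. The study catheter replaces the standard one because of the study, so its recognised complications are what a safety aim should be able to count.

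**Working it through.** The plan gives no power or precision figure for the safety comparison, so there is none to reproduce. The check places the sections side by side and then illustrates the size.

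**Step 1. Which events fall outside the window**

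| Event | Named for monitoring? | Can be recognised after the last device is out? |
|---|---|---|
| Line displacement, accidental extubation | Yes (Aim 1 and/or Adverse events) | No; needs a device in place |
| Ventilator associated pneumonia | Yes (Adverse events) | Yes |
| Catheter associated bloodstream infection | Yes (Adverse events) | Yes |
| Catheter thrombosis | Not by name; could fall under line complications | Yes |

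On the Study Design wording, which stops at extubation, coverage is shorter still for an infant whose line stays in after extubation.

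**Step 2. Inputs for the illustration**

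- From the plan: 20 + 20 = 40 infants.
- Assumed, because the plan gives none of these: true event rates of 10% (study) and 5% (control), a ratio of 2; 200 control infants; and a fraction f of events recognised only after the last device is out.

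**Step 3. Formulas**

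- Control counts all events: apparent ratio = 2(1-f).
- Control loses the same fraction: ratio = 0.10(1-f) / 0.05(1-f) = 2, whatever f is.
- Power in the second case, two-sided 5%, normal approximation: Φ[(d - 1.96·se0)/se1]. Here d is the difference in recorded rates, se0 uses the pooled rate and se1 the separate rates. At f = 0 the pooled rate is (4 + 10)/240 = 0.0583, se0 = 0.0406 and se1 = 0.0499. The result is Φ[(0.05 - 0.0796)/0.0499] = 27.7%.
- Chance of recording no event in 40 infants at a true rate of 5%: (1 - 0.05(1-f))^40.

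**Step 4. Results**

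| f (assumed) | Apparent ratio, only study loses late events | Ratio, both lose equally | Power, both lose equally | P(no event recorded), true rate 5% |
|---|---|---|---|---|
| 0 | 2.0 | 2.0 | 27.7% | 12.9% |
| 10% | 1.8 | 2.0 | 25.9% | 15.9% |
| 25% | 1.5 | 2.0 | 23.3% | 21.7% |
| 30% | 1.4 | 2.0 | 22.4% | 24.0% |
| 50% | 1.0 | 2.0 | 18.7% | 36.3% |

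Unequal windows shrink the ratio. Equal windows with equal late fractions leave it intact, but fewer events are counted and the absolute rate is understated.

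**The case against.** A reader might go further than the documents allow in three ways.

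- **That thrombosis will never be counted.** The monitored line complications are introduced as examples, so the list is open and thrombosis fits the category. It is unnamed and undefined, not excluded. Its absence from the events reported at once to the DSMB adds little: infection and pneumonia are also absent from that list, yet both are monitored. Nor can a rise in thrombosis be inferred from 4.5 versus 4 French, because the plan also describes heparin bonding, a heparin and antimicrobial coating, and a heparin infusion.
- **That the safety conclusion is biased.** This needs a control counted over a longer window, such as whole admissions. The plan does not say so.
- **That all of Aim 1 is affected.** Its named examples cannot occur once the device is out.

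Three further points are fair. Taking the later of the two removals gives some follow-up for the device removed first, so f must count only events found after the second removal. A culture drawn before removal and reported afterwards might still be captured, since laboratory data are extracted with their times; the plan does not settle this. And the safety comparison is weak even with complete follow-up: for 10% versus 5%, power is 13.2% against 40 controls and 27.7% against 200, and 80% power would need 435 per arm. Longer ascertainment will not cure that.

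What remains is that no route is stated for events recognised after the last removal, the control's window is undefined, and a recognised catheter risk is not named for monitoring. A small sample is a reason to avoid losing events, not a reason to accept it.

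**Conclusion.** The point holds as a gap in ascertainment. Followed as written, the plan gives no means of counting a pneumonia, bloodstream infection or clot recognised after both devices are out, although it commits to monitoring the first two. The study's event rate may be understated.

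Bias toward no increase is conditional on the control using a longer window. If it does, and 10% to 30% of study events are recognised late, a true doubling would appear as a ratio of 1.8 to 1.4. The late fraction is an assumption; the plan gives no basis for choosing a value. With equal windows and equal late fractions the cost is lost events and power, not bias. Line displacement and inadvertent extubation are unaffected. The change is worth making because it is cheap, not because a distortion has been shown.

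**What to change.** 1. Keep the end of device monitoring as it is, but extend adverse-event ascertainment by chart review to a fixed point after removal of each device, for example 7 days, or discharge if earlier. The 7 days is illustrative; what matters is that the window is fixed in advance.
2. Define ventilator associated pneumonia and catheter associated bloodstream infection, and apply the identical window and definitions to the retrospective control.
3. Name catheter-related thrombosis, as diagnosed in routine clinical care, among the monitored line complications in the Adverse events section. No extra imaging is implied.
4. Reconcile the Study Design section, which ends measurement at extubation alone, with the SVC saturation monitoring section and the schematic.

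The cost is protocol wording and a few more days of record review per infant by staff who already abstract the chart daily, plus the same review rules for the control records. Clinical care does not change.
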